#### Table 1. Baseline Covariates

Footnotes defined on last page of table

Page 4 of 5

Variable	Measurement				
Other Medications (continued)					
Anti-diabetics					
Insulin	0/1 indicator at study entry				
Non-Insulin	0/1 indicator at study entry				
Cardiac glycosides	0/1 indicator at study entry				
Calcium gluconate	0/1 indicator at study entry				
Fludrocortisone/ Midodrine	0/1 indicator at study entry				
Weight loss prescriptions	0/1 indicator at study entry				
Fludrocortisone/ Midodrine	0/1 indicator at study entry				
Hyperpolarization-activated cyclic nucleotide-gated channel blocker	0/1 indicator at study entry				

Table 1. Baseline Co	variates
----------------------	----------

Page 5 of 5

a Health care utilization will also be evaluated as the following time-varying covariate during the follow-up period, evaluated every three months: occurrence of any outpatient visit over the prior three months, occurrence of any ER visit over the prior three months, and occurrence of any inpatient visit over the prior three months. Continuous measures of heath care utilization will also be considered. Medication utilization will be assessed as the number of unique generic medications dispensed during the interval and number of unique drug classes dispensed during the interval.

#### 8.3.4 Validity and Reliability

We will use validated definitions where appropriate to identify the cardiovascular events that are of interest in this study (Sentinel Initiative, 2018; McCormick et al, 2015; Sherman et al, 2013; Cutrona et al, 2013; Tirschwell and Longstreth, 2012; Quan et al, 2009; Roumie et al, 2008; Tu et al, 2007; McCormick et al, 2015).

The primary algorithm, with a positive predictive value (PPV) of 86% (95% CI: 79%, 91%), to identify acute MI requires an ICD-10-CM diagnosis code of I21.xxx or I22.xxx (see Appendix C) in the principal or primary position of facility claims for hospitalization (Cutrona et al, 2013).

As with acute MI, an algorithm to identify ischemic stroke with good PPV (90% [95% CI: 77%, 97%]) also requires an ICD-10-CM diagnosis code (I63.xxx) occurring in the primary position for facility claims for hospitalization (Tirschwell and Longstreth, 2012). In contrast, the algorithms for intracerebral hemorrhage (PPV – 89% [95% CI: 75%, 99%], ICD-10-CM diagnosis code I61.xxx) and subarachnoid hemorrhage (PPV – 94% [95% CI: 83%, 99%], ICD-10-CM diagnosis code I60.xxx) require a diagnosis code for hemorrhage that can occur in any diagnosis position for an inpatient hospitalization (Tirschwell and Longstreth, 2012). All ischemic and hemorrhagic (intracerebral and subarachnoid) stroke events will be combined to identify 'any stroke' for the primary analysis; however, the cumulative incidence of ischemic and hemorrhagic stroke events will also be described separately.

Algorithms that evaluate acute MI, ischemic stroke, and hemorrhagic stroke in either the emergency room (ER) or the inpatient setting will also be considered.

There are a number of algorithms, with varying performance characteristics, to identify clinical hypertension in administrative claims data (Sherman et al, 2013; Quan et al, 2009; Tu et al, 2007) but none to evaluate drug-induced hypertension. As a result, using the hypertension codes listed in Appendix C, we will evaluate new onset hypertension with the following algorithms:

- 1. 1 IP / 1 ER / 1 OP diagnosis (any position) of hypertension
- 2. 1 IP / 1ER / 1 OP diagnosis (any position) of hypertension, with a prescription fill for an anti-hypertensive medication within 30 days after the hypertension diagnosis date.
- 3. 1 IP / 1ER / 1 OP diagnosis of hypertension (any position), and discontinuation of the study medication within 90 days after diagnosis
- 4. 1 IP / 1 ER / 1 OP diagnosis (any position) of hypertensive crisis
- 5. 1 IP / 1 ER diagnosis of hypertension in the primary position

New onset hypertension will be the primary hypertension outcome of interest, and the cumulative incidence of this outcome will be evaluated at 1 month, at 2 months, at 3 months, at 6 months, and at 12 months. When evaluating new onset hypertension, individuals with a prior history of hypertension during the baseline period will be excluded. For individuals with baseline hypertension and anti-hypertension medication use, we will also evaluate changes in medication dosage or initiation of new anti-hypertensive medications within 90 days after initiation of the study medication.

In addition, we will evaluate the occurrence of a single diagnosis of elevated blood pressure reading, without diagnosis of hypertension (ICD-10-CM diagnosis code R03.0) occurring in any diagnosis position in the IP, ER, or OP setting.

The algorithm used to identify patients with migraine in this study has not been validated, but a similar algorithm (Kolodner et al, 2004) had high specificity and low sensitivity. Thus, it is possible that some migraine patients will be misclassified as non-migraine patients and will be excluded from this study.

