### Decision to Proceed to Comparative Analyses

The decision to move forward with the comparative analysis for either the acute MI or the stroke outcome will be made after assessment of covariate balance across treatment groups (eg, based on an absolute standardized mean difference of > 0.10 for covariates included in the PS model, and adequate overlap in the PS across treatment arms), null findings for the final set of negative control outcomes (ie, posterior probability > 90% that the level of bias is less than 10% of the null), and sufficient sample size to detect a risk ratio of 2.0 or greater. For the relatively rate outcome of acute MI, a total of 15,000 patients in each comparator arm will be needed in order to detect a risk ratio of 2.0 or greater, assuming 80% power and a background rate of acute MI of 0.15 per 100 person-years. In contrast, for the outcome of stroke, 3,750 patients will be required in each treatment arm to detect a risk of 2.0 or greater, assuming 80% power and a background rate of stroke of 0.60 per 100 peson-years.

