### Modeling Assumptions

Results from these analyses will be subject to limitations if certain assumptions of the methods are violated. The assumptions include the following:

- i. Conditional exchangeability, given measured covariates
- ii. No misclassification of the exposure, outcome, or other study variables
- iii. Stable unit treatment value assumption (SUTVA), which requires that outcomes are not correlated
- iv. Consistency, such that exposures can be mapped to well-defined interventions
- v. Positivity, wherein there are at least some exposed and unexposed individuals at each level of the confounders
- vi. No misspecification of the three models considered in these analyses: (a) the structural (ie, weighted) model, (b) the exposure model (ie, the PS model), and (c) the censoring model(s).

Discussion of the impact of violations of these assumptions are deferred to later sections.

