### 8.9 Limitations of the Research Methods

### 8.9.1 Internal Validity of Study Design

### 8.9.1.1 Measurement Error/Misclassification

Measurement error may occur when identifying medication cohorts in claims databases because the presence of a claim for a prescription does not necessarily mean that the medication was taken as prescribed. Also, medication given as free samples by a physician will not be observed in claims data. For the current analyses, measurement error may also occur due to the free drug and coupon programs that have been available after launch of CGRP mAbs. Patient assistance programs are often sponsored by pharmaceutical companies to provide drugs at low or no cost to patients who lack prescription drug coverage for a particular medication. Using a different data source (not claims-based), it has been reported that 76% of the first 64439 new users of erenumab-aooe were covered through "discount/coupon" programs (Hines et al, 2019). Analyses using more recent data show that the majority of erenumab-aooe patients  $(\sim 60\%)$  continue to have coverage using this program. Similar programs have been in place for the other mAbs targeting the CGRP pathway. Although this will result in missing claims, it is not expected that this would introduce bias when assessing claims in relation to the outcomes under study. Care should be taken, however, to ensure that results are not interpreted as risk for the outcome in people who have newly started CGRP mAbs, but rather as risks in people who have a first claim in the database.

Patients who receive medical insurance from federal programs, such as Medicaid, are not eligible to receive additional financial assistance (through the Aimovig™ Ally Card) for erenumab-aooe (with the exception of the Safety Net program for Medicare

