	9.3.3 Covariates and other characteristics?				
9.4	Is a linkage method between data sources described? (eg, based on a unique identifier or other)			$\boxtimes$	

Secti	on 10: Analysis plan	Yes	No	N/A	Section Number
10.1	Are the statistical methods and the reason for their choice described?				8.7.2
10.2	Is study size and/or statistical precision estimated?	$\bowtie$			8.5
10.3	Are descriptive analyses included?	$\square$			8.7.2.3.2
10.4	Are stratified analyses included?	$\square$			8.7.2.5.2
10.5	Does the plan describe methods for analytic control of confounding?	$\boxtimes$			8.7.2.4
10.6	Does the plan describe methods for analytic control of outcome misclassification?		$\boxtimes$		
10.7	Does the plan describe methods for handling missing data?	$\boxtimes$			8.7.2.2
10.8	Are relevant sensitivity analyses described?	$\square$			8.7.2.5

Secti	on 11: Data management and quality control	Yes	No	N/A	Section Number
11.1	Does the protocol provide information on data storage? (eg, software and IT environment, database maintenance and anti-fraud protection, archiving)		$\boxtimes$		
11.2	Are methods of quality assurance described?	$\boxtimes$			8.8
11.3	Is there a system in place for independent review of study results?		$\boxtimes$		

Sect	ion 12: Limitations	Yes	No	N/A	Section Number
12.1	Does the protocol discuss the impact on the study results of:				
	12.1.1 Selection bias?	$\square$			8.9.1
	12.1.2 Information bias?	$\square$			8.9.1
	12.1.3 Residual/unmeasured confounding?	$\boxtimes$			
	(eg, anticipated direction and magnitude of such biases, validation sub-study, use of validation and external data, analytical methods).				8.9.1
12.2	Does the protocol discuss study feasibility? (eg, study size, anticipated exposure uptake, duration of follow-up in a cohort study, patient recruitment, precision of the estimates)				8.5

Comments:

Sect	ion 13: Ethical/data protection issues	Yes	No	N/A	Section Number
13.1	Have requirements of Ethics Committee/ Institutional Review Board been described?			$\boxtimes$	
13.2	Has any outcome of an ethical review procedure been addressed?			$\boxtimes$	
13.3	Have data protection requirements been described?			$\boxtimes$	

Section 14: Amendments and deviations	Yes	No	N/A	Section Number
14.1 Does the protocol include a section to document amendments and deviations?				11

Section 15: Plans for communication of study results	Yes	No	N/A	Section Number

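### The protocol quotes PPVs of 86–94% for its MI and stroke algorithms, then assumes error-free outcomes and plans no bias analysis for the difference

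*Protocol*

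**What the plan says.** Section 8.3.4 supports the outcome definitions with validation figures. For MI: "The primary algorithm, with a positive predictive value (PPV) of 86% (95% CI: 79%, 91%), to identify acute MI requires an ICD-10-CM diagnosis code", in the principal position of an inpatient claim. Ischemic stroke has a PPV of 90% (77%, 97%). Intracerebral hemorrhage is given as "89% [95% CI: 75%, 99%], ICD-10-CM diagnosis code I61.xxx", and subarachnoid hemorrhage as 94% (83%, 99%). The same section says that definitions using emergency room or inpatient codes will also be considered.

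The Modeling Assumptions part of Section 8.7.2.4 lists "No misclassification of the exposure, outcome, or other study variables" and leaves the effect of violations to later sections. Section 8.9.1.1 then opens with "Measurement error may occur when identifying medication cohorts in claims databases" and stays with exposure. Section 8.9.1.2 concerns the indication for the index drug. Section 8.9.3 says in general terms that a code may be wrong or a rule-out diagnosis. In Appendix B, checklist item 10.6 ("Does the plan describe methods for analytic control of outcome misclassification") is answered No.

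Section 8.9.1.4 sets out a formula and parameters for a quantitative correction, but only for an unmeasured confounder (smoking). The sample-size criterion for the comparative analyses reads, for MI, "a total of 15,000 patients in each comparator arm will be needed in order to detect a risk ratio of 2.0 or greater". The figure for stroke is 3,750 per arm.

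**The concern.** By the protocol's own figures, 6–14% of coded MI and stroke events are not true events, so the stated assumption does not hold. The promised discussion of violations gives neither direction nor size for these two outcomes. No calculation uses the PPVs: not Table 3, not the sample-size criterion, not the estimators. The smoking correction needs parameters still to be taken from the literature, whereas the parameters for outcome error, with confidence intervals, are already in the protocol.

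This is a safety study. If false positives are unrelated to treatment, an RR above 1 and an upper confidence limit above 1 are both understated. If false-positive coding differs by arm, a spurious association is possible in either direction. The negative control outcomes (fractures, vaccinations, screening and similar) do not test how MI or stroke is coded, so they are not designed to reveal it.

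**Working it through.** **Inputs.** PPVs from Section 8.3.4. RR 2.0, 80% power, 15,000 (MI) and 3,750 (stroke) per arm, background 0.15 and 0.60 per 100 person-years, from Decision to Proceed to Comparative Analyses. Alpha 0.05 and equal arms from Section 8.5. Assumed, because not stated: two-sided alpha, one person-year per patient, and background rates that are rates of coded events.

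**Reproducing the plan.** Schoenfeld's formula for RR 2.0 gives 66 events.
- MI: 66 / (0.0015 × 3) = 14,667, against 15,000.
- Stroke: 66 / (0.006 × 3) = 3,667, against 3,750.

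Both are within 3%, with no allowance for false positives. A two-proportion calculation at the stated sizes gives power of 78.3% and 78.6%.

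**Case (a): equal false-positive risk F and equal sensitivity Se in both arms.** With true comparator risk I, the observed risks are Se·I + F and RR_true·Se·I + F. Since PPV0 = Se·I / (Se·I + F) in the comparator arm:

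RR_obs = PPV0 × RR_true + (1 − PPV0), so RR_true = (RR_obs − (1 − PPV0)) / PPV0.

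| | MI, PPV 0.86 (0.79–0.91) | Stroke, PPV 0.90 (0.77–0.97) |
|---|---|---|
| True 2.0 is observed as | 1.86 (1.79–1.91) | 1.90 (1.77–1.97) |
| Observed 2.0 needs a true RR of | 2.16 (2.27–2.10) | 2.11 (2.30–2.03) |
| Power at stated size, Schoenfeld | 70% (64–75%) | 74% (62–79%) |
| Power at stated size, two proportions | 67.5% (61–72%) | 71% (60–77%) |
| Size per arm for 80% power | 19,100 to 20,200 | 4,430 to 4,640 |

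The last row runs from Schoenfeld to two proportions at the central PPV. If the background rates are rates of true events, the two-proportion sizes are about 17,360 and 4,170.

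Using 0.90 for all stroke is reasonable. With the rates in Section 6.3 (5.13 ischemic, 1.00 hemorrhagic per 1000 person-years) and the midpoint of 0.89 and 0.94 for hemorrhage, (5.13 × 0.90 + 1.00 × 0.915) / 6.13 = 0.902.

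**Case (b): PPV specified by arm, equal sensitivity.** With PPV1 for erenumab, RR_obs = RR_true × PPV0 / PPV1.
- PPV 86% in both arms: 2.0 stays 2.0 and 1.0 stays 1.0.
- PPV1 79%, PPV0 91%: 1.0 becomes 0.91 / 0.79 = 1.15, and 2.0 becomes 2.30.
- Reversed: 1.0 becomes 0.87, and 2.0 becomes 1.74.

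Both 1.15 and 0.87 lie outside the 0.91–1.10 band that the protocol accepts for bias in its negative control analysis.

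**The case against.** A reader might infer that false positives pull every RR toward 1. A PPV below 100% does not imply that. It needs equal false-positive risk, equal sensitivity and a true RR other than 1, and no passage of the protocol asserts the first two. Nor is the upper limit always too low: under case (a) at PPV 0.86, an observed 0.80 corrects to (0.80 − 0.14) / 0.86 = 0.77, so the observed value was too high. One might also argue for a still lower PPV because this cohort has fewer events than the validation populations, but the protocol gives no incidence for those populations.

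The shift is also modest beside random error. At 15,000 per arm the expected MI counts at RR 2.0 are about 22 and 45, giving a 95% interval of roughly 1.2 to 3.3. The PPVs do serve a purpose, since they support the choice of inpatient definitions. The no-error assumption and the No in the checklist are open disclosures, and a PPV sensitivity analysis could sit in a statistical analysis plan that is not at hand.

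Most of this stands, and it limits the size and direction of the claim. It does not close the gap. The protocol itself promises a discussion that its later sections do not supply for MI and stroke, and itself fixes which biases are quantified. Equal PPV in both arms is not a comfortable default either: at a true RR of 2.0 it would require the drug to double false-positive coding as well.

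**Conclusion.** The point holds in limited form. The protocol reports imperfect PPVs, assumes perfect outcomes, and offers only a generic coding caveat in between. Under equal false-positive risk and equal sensitivity, with the quoted PPVs holding in the comparator arm, the loss is about 0.10–0.14 on an RR of 2.0 and roughly 6 to 12 percentage points of power against the stated 80%. Under equal PPV there is no bias. Under unequal PPV the direction is open; the 79% versus 91% example takes the two ends of one confidence interval and is an illustration, not an estimate. It would therefore be wrong to state flatly that the criterion's 2.0 is really 2.16 or 2.11; those values belong to case (a) only. This is a worthwhile, inexpensive improvement, not a flaw that invalidates the design.

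**What to change.** In Section 8.9.1.4, beside the smoking correction, add an outcome-misclassification bias analysis for each comparative RR and its confidence limits. Use the Section 8.3.4 PPVs and their interval limits in two forms:

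- (a) equal false-positive risk: RR_true = (RR_obs − (1 − PPV0)) / PPV0;
- (b) PPV differing between arms: RR_true = RR_obs × PPV1 / PPV0.

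State that both take sensitivity as equal. In Sections 8.5 and 8.7.2.4, label the detectable RRs and the 2.0 in the sample-size criterion as RRs on coded events. Note there that, under (a), 2.0 corresponds to a true RR of about 2.16 (2.10–2.27) for MI and 2.11 (2.03–2.30) for stroke.

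No new data or patients are needed. The cost is a little more analysis and a wider, less favourable sensitivity range.

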### 8.2.5 Study Follow-up

Follow-up will be evaluated in two ways. With an 'intention-to-treat' analysis, patients will be followed for all available time after they initiate a medication, irrespective of whether they discontinue the medication or not, or whether they switch to an alternate medication or not. Follow-up begins the day after the index date and ends at first occurrence of: (a) the outcome of interest, (b) disenrollment from a health plan, or (c) end of study period.

With a 'per-protocol analysis' patients are followed for as long as they are actively taking the medication of interest during the follow-up period. Follow-up begins the day after the index date and ends at first occurrence of: (a) the outcome of interest, (b) disenrollment from the health plan, (c) discontinuation of study medication, (d) switching to the alternate medication, or (e) administrative end of study. When a gap greater than the allowable gap of 30 days is encountered, discontinuation of study medication occurs at the end of the last prescription which includes the days supply (+60 day extension). Censoring due to switching will occur for the new user cohorts in this study when the following conditions are met:

- (1) For new users of erenumab-aooe, initiation of any other medication targeting the CGRP pathway (galcanezumab-gnlm, fremanezumab-vfrm, eptinezumab-jjmr, ubrogepant, rimegepant) during the follow-up period.
- (2) For new users of other mAbs targeting the CGRP pathway, initiation of erenumab-aooe, ubrogepant, or rimegepant during the follow-up period.
- (3) For new users of the SOC migraine preventive medications (anti-epileptics), initiation of any medication targeting the CGRP pathway (erenumab-aooe, galcanezumab-gnlm, fremanezumab-vfrm, eptinezumab-jjmr, ubrogepant, rimegepant) during the follow-up period.
- (4) For new users of onabotulinumtoxinA, initiation of any medication targeting the CGRP pathway (erenumab-aooe, galcanezumab-gnlm, fremanezumab-vfrm, eptinezumab-jjmr, ubrogepant, rimegepant) during the follow-up period.

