#### Table 1. Baseline Covariates

Footnotes defined on last page of table

Page 2 of 5

Variable	Measurement	
Concomitant Medications		
Overall Medication Utilization a		
Number of unique generic medications dispensed	Continuous, and categorized based on distribution	
Number of unique drug classes dispensed	Continuous, and categorized based on distribution	
Preventive Migraine Medications		
Anti-epileptic agents	0/1 indicator at study entry for Carbamazepine, Gabapentin, Levetiracetam, Pregabalin, Topiramate, valproic acid, divalproex sodium, Zonisamide	
Anti-hypertensive, beta blockers	0/1 indicator at study entry for Atenolol, Bisoprolol, Metoprolol, Nadolol, Nebivolol, Pindolol, Propranolol, Timolol	
Anti-hypertensive, calcium channel blockers	0/1 indicator at study entry for Flunarizine, Verapamil,	
Anti-hypertensive, other	0/1 indicator at study entry for Candesartan, Clonidine, Lisinopril	
Anti-depressants, serotonin norepinephrine reuptake inhibitors	0/1 indicator at study entry for Duloxetine, Desvenlafaxine, Venlafaxine	
Anti-depressants, tri-cyclics	0/1 indicator at study entry for Amitriptyline, Desipramine, Doxepin, Imipramine, Nortriptyline, Protriptyline	
Anti-depressants, selective serotonin reuptake inhibitors	0/1 indicator at study entry for Escitalopram, Citalopram, Sertraline	
Botulinum toxin	0/1 indicator at study entry for AbobotulinumtoxinA, IncobotulinumtoxinA, OnabotulinumtoxinA, RimabotulinumtoxinB	
Other migraine preventive agents	0/1 indicator at study entry for Carisoprodol, Cyproheptadine, Guanfacine, Memantine, Methysergide, Milnacipran, Tizanidine	
Acute Migraine Medications		
Ergotamines	0/1 indicator at study entry for Dihydroergotamine mesylate, Ergotamine tartrate, Ergotamine tartrate + caffeine, Ergotamine tartrate + caffeine + belladonna + pentobarbital	
Triptans	0/1 indicator at study entry for Almotriptan, Eletriptan, Frovatriptan, Naratriptan, Rizatriptan, Sumatriptan (with and without naproxen), Zolmitriptan	

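### Hypertension algorithms 2 and 3 in Section 8.3.4 misclassify as written: a routine refill can satisfy algorithm 2, and the 60-day extension misplaces the stop date in algorithm 3

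*Protocol*

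**What the plan says.** Section 8.3.4 of the protocol notes that claims algorithms exist for clinical hypertension "but none to evaluate drug-induced hypertension", and for that reason sets out five definitions of new-onset hypertension. Algorithm 1 is a single coded diagnosis in any setting, which is also the hypertension outcome in Section 8.3.2. Algorithm 2 adds the condition "with a prescription fill for an anti-hypertensive medication within 30 days after the hypertension diagnosis date". Algorithm 3 instead adds the condition "and discontinuation of the study medication within 90 days after diagnosis".

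For the new-onset analysis, "individuals with a prior history of hypertension during the baseline period will be excluded". Baseline use of antihypertensives is not an exclusion. Table 1 lists several antihypertensives under preventive migraine medications: eight beta blockers, verapamil among the calcium channel blockers, and a further group ("0/1 indicator at study entry for Candesartan, Clonidine, Lisinopril"). Section 6.1 also describes beta blockers and calcium channel blockers as established migraine prophylaxis.

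The protocol defines discontinuation once, in Section 8.2.5, for per-protocol follow-up. The rule applies once a patient's time without supply exceeds 30 days, and it assigns this date: "discontinuation of study medication occurs at the end of the last prescription which includes the days supply (+60 day extension".

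**The concern.** Algorithms 2 and 3 are the only two of the five that add a treatment response to the diagnosis code. Section 8.9.3 warns of rule-out codes, white-coat readings and hypertension caused by migraine pain, so the added condition has to separate real or drug-related hypertension from noise. As written, each condition can be met, or missed, because of dispensing dates alone.

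In algorithm 2, a patient already taking an antihypertensive for migraine, with no hypertension in baseline, stays in the analysis, and the next scheduled refill confirms any hypertension code. In algorithm 3, adding 60 days to the stop date pushes some genuine stops outside the 90-day window. It also places the stop of some patients whose supply had already run out after a diagnosis that came later. These definitions are reported for four cohorts. Capture may differ by cohort if supply length or prior preventive use differs. Section 8.2.2 gives a reason to expect that prior preventive use may differ, since it cites guidelines under which two standard preventives are tried before erenumab.

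**Working it through.** The protocol gives no figure to reproduce here; the check is date arithmetic on its own rules. The 30-day, 90-day and +60-day terms come from Sections 8.3.4 and 8.2.5. Days of supply is a claims field named in Section 8.4 with no values given, so supply lengths from 28 to 90 days are assumptions.

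**Algorithm 2.** Take a patient who refills an antihypertensive every S days, with the diagnosis equally likely on any day of the cycle. The chance that a routine refill falls in the 30 days after diagnosis is min(1, 30/S):

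- S = 30: 30/30 = 100%
- S = 60: 30/60 = 50%
- S = 90: 30/90 = 33%

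For illustration, assume that 10% to 30% of algorithm 1 cases take such a preventive (the protocol gives no prevalence). The share of those cases meeting algorithm 2 through a routine refill alone would run from 0.10 × 0.33 = 3% to 0.30 × 1.00 = 30%.

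**Algorithm 3.** Let the last fill have supply S, with the diagnosis d days after it and no later fill. The Section 8.2.5 stop date is day S + 60, so the lag from diagnosis to stop is L = S + 60 − d. The case counts if 0 ≤ L ≤ 90, that is, if S − 30 ≤ d ≤ S + 60 (with d not below 0). On-supply days are d = 0 to S − 1; post-supply days are d = S + 1 to S + 60.

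| Supply S | Qualifying days d | On-supply days missed | Share missed | Post-supply days counted |
|---|---|---|---|---|
| 28 | 0 to 88 | 0 of 28 | 0% | 60 |
| 30 | 0 to 90 | 0 of 30 | 0% | 60 |
| 60 | 30 to 120 | 30 of 60 | 50% | 60 |
| 84 | 54 to 144 | 54 of 84 | 64% | 60 |
| 90 | 60 to 150 | 60 of 90 | 67% | 60 |

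The shares missed treat the diagnosis as equally likely on any on-supply day.

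Two cases show the mechanism:

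- **Missed:** S = 90, diagnosis on day 10, no further fill. The stop date is day 150, which is 140 days after diagnosis, so the case is not counted.
- **Counted:** S = 30, supply ends on day 30, diagnosis on day 85. The stop date is day 90, which is 5 days after diagnosis, so the case counts although supply ended 55 days before the diagnosis.

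**The case against.** **Reach.** Algorithm 1 carries no fill or stopping condition and is untouched. Algorithms 2 and 3 select from algorithm 1 cases, so a refill cannot create a case that algorithm 1 did not already count. Formal comparisons are planned only for acute MI and stroke. All of this stands. A reader might infer that the main hypertension estimate is unsound, or that differences between cohorts would simply reflect dispensing patterns. The documents support neither: they give no supply lengths and no preventive use by cohort.

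**Half-life rationale.** The comment in Section 5 of the Appendix B checklist justifies the 30 + 60 day window as approximating erenumab's half-life, so treating post-supply days as exposed is deliberate. That supports an exposure window for censoring. It does not make the extended date a test of whether stopping followed the diagnosis, and it is given for erenumab alone, while algorithm 3 serves all four cohorts.

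**Assumed link.** Section 8.3.4 does not cite Section 8.2.5, and a separate date might be set elsewhere. This stands as a condition on the algorithm 3 figures. Section 8.2.5 is, however, the only definition in the protocol.

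**Prior history.** The exclusion might be read to cover antihypertensive use. The sentence that follows it in Section 8.3.4 names baseline hypertension and antihypertensive use as two separate conditions, and Table 1 lists them separately, so the narrower reading is the natural one.

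**Baseline hypertensives.** A reader might extend the algorithm 2 problem to the 90-day analysis of patients with baseline hypertension. That does not hold. The analysis already asks for new agents or dose changes, so routine refills do not qualify.

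**Conclusion.** The point holds for two of the five new-onset definitions. Followed exactly, algorithm 2 lets a scheduled refill of a migraine preventive confirm a hypertension code; the chance of such a refill is about 100%, 50% and 33% at assumed 30-, 60- and 90-day fills under regular refilling. Algorithm 3 misses about half of on-supply immediate stoppers at an assumed 60-day supply and about two thirds at 90 days, and none at 30 days or less. At every supply length it counts diagnoses made 1 to 60 days after supply ended, if no later fill follows. Those 60 calendar days should not be read as a share of patients, since the documents do not say how diagnoses are spread over them.

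The algorithm 3 result assumes that the Section 8.2.5 date governs. If it does not, the protocol gives algorithm 3 no definition of discontinuation. Capture under both algorithms may differ by cohort if supply length or prior preventive use differs; nothing stronger can be said. The change should be made, but the study's main hypertension outcome does not depend on it.

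**What to change.** **Algorithm 2.** Require a fill of an antihypertensive agent that was not dispensed in the 365-day baseline period, and report the any-fill version alongside it. Routine refills of an established preventive then cannot qualify. The stricter version drops cases managed by raising the dose of an agent already in use, and a new agent started for migraine would still count. Showing both versions makes the effect visible.

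**Algorithm 3.** For this outcome definition only, require the diagnosis to fall within the days' supply of a study-medication fill, and define stopping as no further fill of the study medication after the diagnosis, without the 60-day extension. On-supply immediate stoppers are then captured at any supply length, and diagnoses after supply ended are not counted. Keep the Section 8.2.5 rule for per-protocol censoring.

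Dating the stop at end of supply while keeping the 90-day window would not be enough. A patient on 30-day fills could refill up to 60 days after diagnosis and still count (60 + 30 = 90), whereas a patient on 90-day fills could not refill at all after the diagnosis date. The price of the no-further-fill rule is that patients who stop after one more fill are not counted, and the text should state how much enrolled time after diagnosis is needed to establish that no fill occurred.

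The cost is protocol wording and two code-level definitions, using fill dates and days of supply that Section 8.4 lists among the claims fields.
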